5.0 Study Procedures

Pre-screening survey: Potential participants may choose to complete a pre-screening survey that will better evaluate their eligibility. Subjects may complete the survey on their own or while in clinic.

Screening evaluation: Patient will be consented by phone. We will review the pre-surgical evaluation to assess for inclusion/exclusion criteria and we will invite to complete additional visits in the center for surgical weight loss or the autonomic cardiovascular suite.

Visit 1: Baseline (pre-surgery, RYGB/VSG) or pre-hypocaloric diet (medical weight loss).

Visit 2: After 10% weight loss. The time is variable (RYGB/VSG= 10-12 days; medical weight loss group= \sim 30-40 days).

Visit 3 (only for RYGB and VSG groups): 3-months after the bariatric procedure.

Visit 4 (only for RYGB and VSG groups): After 3-days on stable doses of Strattera (atomoxetine) vs. matching placebo. For the two, parallel-arm, placebo-controlled portion of the study. We will randomize 1:1 to either placebo vs. the NE-transporter inhibitor, Strattera (atomoxetine), at doses of 0.5 mg/kg/day.

Visits 1-4 specific procedures:

In supine position, we will measure: 1) plasma volume assessment; 2) continuous beat-to-beat blood pressure, and heart rate monitoring; 3) muscle sympathetic nerve activity (MSNA) with microneurography (at the physician's descretion), 4) blood volume assessment; and 5) supine plasma catecholamines and metabolites.^{2, 16} We will assess orthostatic tolerance using tilt table testing.^{17, 18} We will perform a 60° head-up tilt (HUT) for 30 min until pre-syncope (defined as systolic BP (SBP, mm Hg) <80 or SBP>90 and pre-syncopal symptoms (nausea, lightheadedness, dizziness).¹⁹ We will repeat plasma catecholamines at the end of the 30 min HUT and hemodynamic measurements throughout the HUT. The supine and 60° HUT plasma catecholamines will provide information on orthostatic-induced sympathetic neuro-hormonal activation. We will use the ratio dihydoxyphenylglycol (DHPG) to NE as the biomarker for NET inhibition as we previously reported.²⁰ We will repeat the serum pregnancy test (if applicable).

We will wait 24 hours to perform visits 1-4 if the patient has received IV fluids for clinical care.

Our primary endpoint (orthostatic tolerance, OT) is defined as the time between the start of the 30° HUT until pre-syncope

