9.0 Statistical Considerations

Sample size justification: For aim 1, we will compare primary endpoint (OT) between each surgery group (RYGB and VSG) and the medical weight loss group. Based on the literature,²² we expect a 48.5% reduction in orthostatic tolerance (OT) after RYGB/VSG (normal baseline OT is 36.7 ± 7.3 (mean±SD) versus poor OT 18.9 ± 5.96 .²²) After weight loss, we estimated a $\approx 25\%$ reduction in OT (baseline 36.7 ± 7.3 to 27.5 ± 7). This is a 25% difference in OT between surgical versus medical weight loss. We need n=15 per group to have 90% power to detect the difference between 18.9 and 27.5 using SD of 7 with type I error rate of 0.05. We plan to enroll 15 subjects in each of the 3 groups. For aim 2, in visit 3 we will randomize these 30 RYGB/VSG subjects with 1:1 ratio to the Strattera and placebo groups. We will compare OT between the placebo and the Strattera groups. We expect that OT is 18.9 ± 5.96 (mean±SD) for the placebo group (similar to the surgery group in aim 1) and the Strattera group will improve by $\approx 50\%$ or 28.35 ± 7 (mean±SD). With 15 in each group in aim 2, we will have excellent (96%) power to detect the difference.

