Data Analysis Plan: the primary analyses will focus on the comparison of the primary endpoint, OT. In aim 1 between RYGB vs. medical weight loss, and between VSG vs. medical weight loss; in aim 2: between Strattera versus placebo groups. Secondary endpoints include changes in hemodynamics (blood pressure, heart rate) during HUT and HUT+LBNP, orthostatic changes in plasma catecholamines, and MSNA. We will assess continuous outcomes for normality. If normality is violated, we will apply data transformation or non-parametric analysis methods. We will provide summary statistics for both numerical and categorical variables by study arms and assess comparability among randomization groups. In both aims, we will estimate the direct between-group difference by means with its 95% confidence interval (CI), which will be tested using either two-sample t-test or Wilcoxon Rank Sum test. A multivariate general linear model will be used to evaluate the group or treatment effects while adjusting the baseline measure of the endpoint. Model over fitting will be avoided using the rule of thumb of 10 observations per parameter in the model. Analyses of secondary endpoints and other exploratory analyses will be conducted similarly. We will test all hypothesis at the level of α =0.05. We will use SPSS for Windows (Version 22.0, SPSS, Chicago) and the open source statistical package R (version 3.4.3, R Core Team, 2017) for analyses (https://www.R-project.org.)

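### OT is to be analysed both unadjusted and baseline-adjusted with neither named as deciding, and the Aim 2 baseline visit is not defined although OT is measured at Visit 3, where randomisation takes place

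*Combined protocol and SAP*

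**What the plan says.** The Data Analysis Plan in section 9.0 makes OT the primary endpoint and names the contrasts: RYGB against medical weight loss and VSG against medical weight loss (Aim 1), and Strattera against placebo (Aim 2). For both aims it plans the difference in means with a 95% CI, "which will be tested using either two-sample t-test or Wilcoxon Rank Sum test". The next sentence reads "A multivariate general linear model will be used to evaluate the group or treatment effects while adjusting the baseline measure of the endpoint". Two further sentences affect the choice: "If normality is violated, we will apply data transformation or non-parametric analysis methods" and "Model over fitting will be avoided using the rule of thumb of 10 observations per parameter in the model". All hypotheses are tested at 0.05. Neither analysis is called primary, supportive or sensitivity.

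On baseline, section 5.0 has "Visit 1: Baseline (pre-surgery, RYGB/VSG) or pre-hypocaloric diet (medical weight loss"; no other visit carries that label. The sample size text in section 9.0 also uses the word for OT before weight loss (36.7 ± 7.3). For Aim 2 the same section says "in visit 3 we will randomize these 30 RYGB/VSG subjects with 1:1 ratio to the Strattera and placebo groups". Under "Visits 1-4 specific procedures", section 5.0 states "We will assess orthostatic tolerance using tilt table testing", so OT is measured at Visit 3, before study drug, and again at Visit 4 after three days on it.

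**The concern.** Two analyses address the same effect on the same primary endpoint, and they can disagree. The order of the text and the sample size lean towards the unadjusted test, but a lean is not a rule. With no hierarchy, the more favourable result could be reported as the primary one.

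The second gap is the covariate. Read literally, the Aim 2 model would adjust for OT taken before surgery, more than three months before the outcome and on the far side of the change that Aim 1 expects surgery to cause. Visit 3 OT is the pre-treatment value and costs nothing extra. A covariate helps at this sample size only if its correlation with the outcome is above about 0.2, so the choice of visit matters. In Aim 1, which is not randomised, adjusting for Visit 1 OT can reduce bias from differences in starting OT, though not from other differences between the groups.

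**Working it through.** **1. The plan's own figures.** Two-sample t-test, noncentral t, 15 per group, two-sided 0.05 (sidedness is not stated and is assumed).
- Aim 1: difference 27.5 − 18.9 = 8.6, SD 7. Power 90.1%, against 90% stated.
- Aim 2: difference 28.35 − 18.9 = 9.45, pooled SD √((5.96² + 7²)/2) = 6.50. Power 97.0%, against 96% stated (94.6% with SD 7 in both arms).

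Both figures reproduce, and both are unadjusted calculations.

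**2. When adjustment pays in Aim 2.** Let r be the correlation between Visit 3 and Visit 4 OT.
- Unadjusted half-width ≈ t(28) × 6.50 × √(2/15) = 2.048 × 6.50 × 0.365 = 4.86 min.
- Adjusted half-width ≈ t(27) × 6.50 × √(1 − r²) × √(2/15) × √(27/26). The last factor is the average cost of chance imbalance in the covariate. At r = 0.5: 2.052 × 6.50 × 0.866 × 0.365 × 1.019 = 4.30 min.
- Break-even: 1 − r² = (2.048/2.052)² × 26/27 ≈ 0.96, so r ≈ 0.2.

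Simulation gives mean half-widths slightly below these approximations (4.82 and 4.26 min) and the same break-even.

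**3. Simulated results, 15 per group.** OT is normal with the means and SDs of section 9.0. Section 5.0 describes a 30-min tilt, but section 9.0 plans around a mean of 36.7 and mentions an added LBNP stage that section 5.0 does not describe. Both readings are therefore shown: uncapped, and with every OT value cut at 30 min. In the capped rows r is the correlation before the cut. Half-widths are at the planned effects.

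| Quantity | Unadjusted | r = 0.3 | r = 0.5 | r = 0.7 |
|---|---|---|---|---|
| Aim 2 half-width (min), uncapped | 4.8 | 4.7 | 4.3 | 3.5 |
| Aim 2 half-width (min), capped | 3.9 | 3.8 | 3.5 | 3.0 |
| Aim 2 power at half effect (4.725 min), uncapped | 48% | 51% | 59% | 75% |
| Aim 2 power at half effect, capped | 46% | 48% | 55% | 70% |
| Aim 1 half-width (min), uncapped | 5.2 | 5.1 | 4.6 | 3.8 |
| Aim 1 half-width (min), capped | 4.3 | 4.3 | 4.2 | 3.9 |
| Aim 1 power, uncapped | 90% | 92% | 96% | 99% |
| Aim 1 power, capped | 88% | 88% | 90% | 94% |

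The cap compresses OT, so capped and uncapped rows should not be compared with each other; only the comparison along a row is informative. At r = 0 the adjusted Aim 2 half-width is 4.9 min against 4.8 (uncapped).

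**4. Why Aim 1 gains little under a cap.** The share of Visit 1 values above 30 min is 1 − Φ((30 − 36.7)/7.3) = 1 − Φ(−0.92) ≈ 82%, so the covariate is nearly constant. At Visit 3 the share is 1 − Φ((30 − 18.9)/5.96) = 1 − Φ(1.86) ≈ 3%, so the Aim 2 covariate keeps its information.

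**5. Type I error if the choice stays open (Aim 2).** Each analysis alone holds about 5%. Counting success on either the t-test or the Visit 3-adjusted model gives about 6.4%, 7.4% and 8.3% at r = 0.3, 0.5 and 0.7. Adding a Visit 1-adjusted model gives 8.2% to 10.1% (assumed correlations with Visit 4: 0.2 to 0.5 for Visit 1, 0.5 to 0.7 for Visit 3). At half the planned effect, the t-test and the Visit 3-adjusted model disagree on significance in about 10%, 19% and 33% of simulated trials.

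**6. The parameter rule.** Treatment plus one baseline in 30 subjects is 30/2 = 15 per term, or 30/3 = 10 with the intercept counted. That leaves no room for both Visit 1 and Visit 3 OT.

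**The case against.** The unadjusted test comes first in the text and carries the sample size. Naming it primary would also close the multiplicity gap, so preferring the adjusted model is partly a choice about efficiency. That stands: the essential request is one named analysis. The efficiency case rests on assumed correlations, and at r = 0.3 the Aim 2 gain is only 0.1 min. At the planned effect, uncapped power is already about 97%, so the gain lies in precision and in smaller effects.

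It can also be said that the baseline for a randomised treatment effect is ordinarily the pre-treatment value, so Visit 3 is implied. That is reasonable, but the only labelled baseline points elsewhere, and one sentence would settle it.

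If OT is capped, about 41% of Strattera Visit 4 values and 36% of medical-group Visit 2 values would sit at 30 min on the planning figures. Normality would then probably fail and the fallback could become the main analysis. This stands, and it is why the fallback and its trigger need fixing in advance.

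A reader might infer more than the documents support:
- That the sample size is wrong. It reproduces.
- That adjusting Aim 2 for Visit 1 OT would be biased. Under randomisation it is valid, only probably less efficient.
- That the trial will run at an inflated error rate. The excess arises only if the result is picked after the fact, and nothing in the documents says that it will be.
- That 8.3% is an upper limit. It counts two analyses; Visit 1 adjustment, the Wilcoxon test and transformation would add to it.
- That Aim 1 gains as much as Aim 2. Under a 30-min cap it gains almost nothing at r = 0.3.

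**Conclusion.** The point holds as a gap in specification with a low-cost improvement attached; it is not an arithmetic error or an invalid analysis. The plan does not say which of two analyses decides OT, and it does not define the Aim 2 baseline although the natural one is already measured. In Aim 2, adjusting for Visit 3 OT shortens the interval by about 0.1 to 1.3 min uncapped, or 0.1 to 0.9 min capped, for r from 0.3 to 0.7. The Aim 1 gain is 0.1 to 1.4 min uncapped but at most about 0.4 min capped. All of this rests on assumed correlations and on normal OT before any cap. The change should be made before the data are analysed.

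**What to change.** Amend the Data Analysis Plan as follows:
- Make the already planned baseline-adjusted linear model the single primary analysis for each aim, with the t-test or Wilcoxon test supportive.
- Aim 2: Visit 4 OT on treatment plus Visit 3 OT. State that the Aim 2 baseline is Visit 3.
- Aim 1, for each surgery group against medical weight loss: Visit 2 OT on group plus Visit 1 OT. Visit 2 is the only post-baseline visit that all three groups share.
- Name one fallback, and the criterion that triggers it, for OT that is clearly non-normal or piles up at the tilt limit. The same model on ranks is one option within the plan's existing wording. In uncapped Aim 2 simulations it held type I error at 5.0% to 5.2%, with half-effect power of 49%, 55% and 69% at r = 0.3, 0.5 and 0.7; it was not tested on capped data. A rank model does not give the promised difference in means, so the plan should say how that estimate will be reported.
- State how parameters are counted for the 10-per-parameter rule. With the intercept counted, 30 subjects only just meet it, and one missing subject gives 29/3 = 9.7.

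The cost is wording, one degree of freedom and about 0.1 min of half-width if the correlation is near zero. No new data are needed.

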10.0 Privacy/Confidentiality Issues

All data will be collected specifically for the proposed research project. A unique identification case number will be used to protect the confidentiality of the study participants. Only case numbers will be included in spreadsheets used for the statistical analysis. PHI and access to the key for the ID numbers will only be viewable by members of the research team. Members of the research team will have access to the patient's medical record during the screening visit and throughout the study until the patient completes her participation in the study or meets any of the criteria for study withdrawal/discontinuation.

